8.4.5 Pharmacodynamics

The changes from Baseline in ANC, the number of CANs, and the levels of serum CD62L, serum iFABP, serum LPS, serum hsCRP, and urine 3-indoxyl sulfate will be summarized by dose within formulation and combined placebo.

A dose-response analysis may be conducted to determine the relationship between daily rifaximin ER and DER dosing and reduction of CANs. Dose-response relationships following the final dose on Day 29 may also be assessed for other PD endpoints, if warranted.

The relationship between rifaximin PK parameters (C_{trough}, C_{max,ss}, C_{ss,avg}) and each PD endpoint (ANC, CANs, serum CD62L levels, serum hsCRP, serum iFABP, serum LPS and urine 3-inoxy1 sulfate) may be evaluated following the final dose on Day 29. Additionally, a population PK/PD model may be developed as a separate analysis to explore exposure-response. If conducted, this analysis will be reported separately from the Clinical Study Report.

8.4.6 Analysis of Safety

All adverse events occurring during the study will be recorded and classified based on MedDRA terminology. Only adverse events that occur after the start of study drug, (treatment emergent adverse events [TEAEs]); all AEs will be included in by-subject listings.

TEAEs will be summarized for the entire population, by dose within formulation and combined placebo, and by severity and relationship to study medication. Each subject will be counted only once within a system organ class or a preferred term by using the adverse event with the highest severity or greatest relationship, respectively, within each category.

Treatment-emergent AEs will be summarized as follows:

- Number and percentage of subjects experiencing TEAEs,
- Number and percentage of TEAEs by relationship to study treatment (i.e., related or unrelated),
- Number and percentage of TEAEs by severity,
- Number and percentage of subjects experiencing serious AEs (SAEs),
- Number and percentage of subjects experiencing study drug-related SAEs,
- TEAE leading to permanent treatment discontinuation,
- TEAEs with an outcome of death.

All SAEs, AEs leading to premature withdrawal from the study, and all deaths, will be listed.

Reports of diarrhea due to *C. difficile* will be summarized.

Vital signs will include supine blood pressure (mmHg), heart rate (beats per minute), body temperature, and O₂ saturation. Vital signs will be summarized at Baseline and for each day when vital signs were obtained. Changes from Baseline in vital sign measurements will also be summarized. For each summary the N, mean, median, SD, minimum, and maximum values will be given for all subjects, by dose within formulation and combined placebo. Pretreatment vital signs obtained closest in time to first dose of study drug will be used for summarization and analysis of Baseline and change from Baseline vital signs.

Changes from Baseline in abbreviated physical exam findings of clinical significance will be summarized and listed.

8.4.7 Clinical Safety Laboratory Findings

Clinical safety laboratory data (hematology, chemistry, and urinalysis) will be summarized at Baseline and at each visit per the schedule of assessments, as well as changes from Baseline in laboratory parameters. For each summary the N, mean, median, SD, minimum, and maximum values will be given by dose within formulation and combined placebo. Pretreatment laboratory values obtained closest in time to first dose of study drug will be used for summarization of Baseline and change from Baseline. Pregnancy testing results (urine and serum) will be presented in by-subject listings.

Clinical safety laboratory tests performed during the study will be primarily analyzed by a central clinical laboratory.

8.4.8 ECG Findings

ECGs with abnormal findings will be summarized and listed.

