	
Baseline (pre-dose at Day 1) at each visit for which they are collected.
 
iFABP, LPS, hsCRP, and urine 3-indoxyl sulfate levels will be summarized by treatment with descriptive statistics and change from Baseline (pre-dose at Day 1) at each visit.
 
A dose-response analysis may be conducted to determine the relationship between daily rifaximin ER and DER dosing and reduction of CANs. Dose-response relationships following the final dose on Day 29 may also be assessed for other PD endpoints, if warranted.
 
The relationship between rifaximin PK parameters (C_{trough}, $C_{max,ss}$, $C_{ss,avg}$) and each PD endpoint (ANC, CANs, serum CD62L levels, serum iFABP, serum LPS, serum hsCRP, and urine 3-inoxy sulfat) may be evaluated following the final dose on Day 29. Additionally, a population PK/PD model may be developed as a separate analysis to explore exposure-response. If conducted, this analysis will be reported separately from the Clinical Study Report.
 
Safety:
 
All AEs occurring during the study will be recorded and classified based on MedDRA terminology. Adverse events that occur after the start of treatment (treatment-emergent adverse events [TEAEs]), will be summarized; all AEs will be included in by-subject listings.
 
TEAEs will be summarized for the entire population, by treatment group, and by severity and relationship to study medication. Each subject will be counted only once within a system organ class or a preferred term by using the adverse event with the highest severity or greatest relationship, respectively, within each category. All SAEs, AEs leading to premature withdrawal from the study, and all deaths will be listed.
 
Vital signs will be summarized at Baseline and for each visit. Changes from Baseline in vital sign measurements will also be summarized.
 
Clinical safety laboratory data will be summarized at Baseline, at each visit, and as changes from Baseline in laboratory parameters. Abnormal findings in ECGs and physical examinations will be summarized and listed.
 
Data permitting, the number and duration of VOCs (overall and by subcategory) and SCD-associated medical facility visits that do

--	---

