17. Subject has a bleeding disorder including, but not limited to, acquired or congenital platelet function defects, disseminated intravascular coagulation (DIC), bleeding factor deficiencies, hemophilia, idiopathic thrombocytopenia purpura (ITP), or von Willebrand's disease.
18. Subject is planning to undergo a major surgical procedure during the duration of the study.
19. Subject has a positive test for human immunodeficiency virus (HIV)1 or HIV2.
20. Subject has an active Hepatitis B infection (HBsAg positive). Prior infection that is not active (i.e., HBsAg negative, HBcAb positive, and HBsAb positive) is permitted.
21. Subject has a positive test for Hepatitis C (HCV RNA). Prior infection with spontaneous resolution or sustained resolution for ≥ 24 weeks after cessation of antivirals is permitted.
22. Subject has an active COVID-19 infection or complication(s) related to COVID-19 infection that are unresolved or, in the opinion of the Investigator, may affect evaluation of the study drug or place the subject at undue risk.
23. Subjects has received a vaccine (including COVID-19 vaccine) within 2 weeks prior to Screening. If subject has received their first of two COVID-19 vaccination doses, as applicable, they must wait for at least 2 weeks after receiving the second dose, and be symptom-free, prior to beginning Screening. Subject must not be planning for COVID-19 or other vaccinations while on study.
24. Subject has a malignant disease. Exceptions include malignancies that were treated curatively and have not recurred within 2 years prior to study treatment, completely resected basal cell and squamous cell skin cancers, and any completely resected carcinoma in situ.
25. Subjects has prolonged QT interval as assessed by ECG history within the past 3 months. For subjects with no historical ECG information, subject has a resting QTcF ≥ 460 msec for males and ≥ 470 msec for females at Screening.
26. Subject has any unstable cardiac condition that, in the opinion of the Investigator, may worsen during the study or interfere with successful evaluation of the study treatment.
27. Subject has a serious mental or physical illness which, in the opinion of the Investigator, would compromise participation in the study.
28. Subject has any condition which, in the opinion of the Investigator, is likely to interfere with the successful collection of the measurements required for the study.

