6.1.8 Visit 9 (Day 43 ± 3 days) EOS Visit

The following assessments are to be completed at the EOS Visit:

- Collect any adverse events since Visit 8.
- Collect concomitant medication changes since Visit 8. Specifically collect opioid use since Visit 8.
- Obtain subject's weight.
- Obtain vital sign measurements (BP, HR, body temperature, and O₂ saturation.)
- Conduct symptom-directed physical exam, as needed.
- Obtain ECG (12-lead) if abnormal findings were observed at Visit 5 (Day 29).
- Conduct urine pregnancy test for WOCBP.

- Collect blood samples for hematology and blood chemistry and urine for urinalysis only if needed for follow-up of AEs or SAEs.
- Collect blood samples for CANs, CD62L, iFABP and LPS.
- Collect urine sample for 3-indoxyl sulfate
- Query subject and record VOCs that have occurred since Visit 5.
- Record any concomitant medications.
- Record any adverse events.
- Discharge subject from study. Follow subject for AEs or SAEs as described in Section 7.7.

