6.2.3.5 Electrocardiogram (ECG)

A 12-lead ECG (Supine) will be performed on all subjects using a standard ECG machine at Visit 1, (Screening), Visit 2 (Baseline), Visit 5 (Day 29/EOT/ET), and Visit 9 (Day 43/EOS), if applicable.

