- b. Medical history will be obtained from prior 3 months. Detailed history of VOCs occurring over the past 12 months will be obtained. This will include collection of treatments for VOCs including drug, dose, route of admin, duration of treatment, and inpatient/outpatient setting.
- c. Vital signs will be obtained after the subject has been in a supine position for a minimum of 5 minutes. Vital signs include systolic and diastolic blood pressure, heart rate, body temperature, and oxygen saturation.
- d. Perform a full physical examination at Screening and symptom-directed physical examination at subsequent visits.
- e. A 12-lead ECG (supine) will be performed. An ECG will be performed at the Day 43 (EOS) Visit only if abnormal findings were observed at the Day 29 (EOT/ET) Visit.
- f. Hemoglobin genotyping will be recorded if known. If unknown at Screening, hemoglobin genotyping will be performed using HPLC/electrophoresis.
- g. Serum pregnancy test is to be performed at Screening for all women of childbearing potential. A negative Screening serum pregnancy test and a negative urine pregnancy test must be confirmed before randomization. Subsequent pregnancy testing will be with urine pregnancy test.
- h. Information on whether a VOC requiring a visit to a medical facility occurred will be recorded. Medications received during the VOC visit will be recorded.
- i. Only weight will be collected.
- j. Hematology, chemistry, and/or urinalysis will only be collected at this visit if needed for follow-up or resolution of AEs/SAEs.
- k. Not all treatment groups will return study drug at Visit 3 and Visit 4.
- l. During Screening, record all opioid use for the prior 30 days. At each visit, record all opioid use since the previous visit.

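### The planned ECG summary covers abnormal tracings only, with no Baseline comparison and no intervals, so it neither separates new from pre-existing abnormalities nor shows a QTcF shift short of an abnormal call

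*Combined protocol and SAP*

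**What the plan says.** Section 8.4.8 is a single sentence: "ECGs with abnormal findings will be summarized and listed". The Safety paragraph of the synopsis's statistical methodology adds nothing: "Abnormal findings in ECGs and physical examinations will be summarized and listed".

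On collection, Section 6.2.3.5 schedules a supine 12-lead ECG for all subjects at Screening, then at "Visit 2 (Baseline), Visit 5 (Day 29/EOT/ET), and Visit 9 (Day 43/EOS), if applicable". The Day 43 tracing is conditional. Section 6.1.8 reads "Obtain ECG (12-lead) if abnormal findings were observed at Visit 5 (Day 29" and Appendix 1, footnote e, reads "An ECG will be performed at the Day 43 (EOS) Visit only if abnormal findings were observed at the Day 29 (EOT/ET) Visit". Neither requires the Day 29 abnormality to be new.

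QTcF appears only in exclusion 25 (Section 4.2), which first uses history: "Subjects has prolonged QT interval as assessed by ECG history within the past 3 months". The 460/470 msec limits then apply at Screening to the remainder: "For subjects with no historical ECG information, subject has a resting QTcF". Exclusion 26 covers unstable cardiac conditions. No criterion excludes other ECG abnormalities as such.

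**The concern.** Subjects can enter the trial with an abnormal tracing. If the summary is simply of abnormal ECGs, a finding that was there on Day 1 and one that arose on treatment look alike. With 12 subjects per active arm, one or two pre-existing findings are enough to make arms look different, or to hide a real difference.

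The second loss is the interval data. A drift in QTcF across an arm that stays short of an abnormal call in each subject does not appear in this summary. Safety and tolerability are a stated objective, and the tracings needed to look at both questions are already scheduled in every subject.

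**Working it through.** The plan gives no ECG figure, SD, alpha or power, so there is nothing of its own to reproduce beyond the allocation: 4 × 12 + 2 × 6 = 60, consistent with 2:2:1:2:2:1 (Sections 3.2 and 8.2). Combined placebo is 6 + 6 = 12 (Section 8.4.1).

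**1. How each safety assessment refers to Baseline**

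| Assessment | Section | Reference to Baseline |
|---|---|---|
| Adverse events | 8.4.6 | Summaries are of events after start of study drug |
| Vital signs | 8.4.6 | Baseline, each day measured, and change from Baseline |
| Laboratory | 8.4.7 | Baseline, each visit, and change from Baseline |
| Physical examination | 8.4.6, 8.4.9 | Change from Baseline in clinically significant findings, plus abnormal findings |
| ECG | 8.4.8 | None |

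ECG is the only one of the five whose analysis text has no pre-treatment reference. Section 8.0 defines Baseline as the last value before first dose, and a Day 1 ECG is scheduled before randomization (Section 6.1.2), so a paired comparison is available.

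**2. What a count without a Baseline reference can contain (illustration)**

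Let b be the proportion abnormal at Baseline and q the proportion of Baseline-normal subjects who become abnormal. Assume Baseline abnormalities persist to Day 29. Values of b and q are assumptions; the documents give none.

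Expected abnormal at Day 29 in an arm of 12 = 12 × [b + (1 − b) × q]. Share already present = b / [b + (1 − b) × q].

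| b | Count, q = 0 | Count, q = 0.10 | Share already present, q = 0.10 |
|---|---|---|---|
| 0.20 | 12 × 0.20 = 2.4 | 12 × 0.28 = 3.4 | 0.20/0.28 = 71% |
| 0.40 | 12 × 0.40 = 4.8 | 12 × 0.46 = 5.5 | 0.40/0.46 = 87% |
| 0.60 | 12 × 0.60 = 7.2 | 12 × 0.64 = 7.7 | 0.60/0.64 = 94% |

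With no drug effect (q = 0), and treating two arms as independent binomial counts with n = 12, the arms differ by at least 2 abnormal subjects with probability 0.44, 0.53 and 0.53 for b = 0.20, 0.40 and 0.60. They differ by at least 3 with probability 0.20, 0.30 and 0.30. Such gaps would come entirely from Baseline.

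**3. What a QTcF change summary would deliver (illustration)**

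Assume an SD of change from Baseline of 15 to 20 msec; the documents give none.

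- Within one arm of 12: t(11, 0.975) × SD / √12 = 2.201 × 15 / 3.464 = 9.5 msec, and 12.7 msec at SD 20.
- One arm of 12 against combined placebo of 12: t(22, 0.975) × SD × √(2/12) = 2.074 × 15 × 0.408 = 12.7 msec, and 16.9 msec at SD 20.

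These describe the arms as the plan reports them, by dose within formulation.

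**4. Timing of the Day 29 ECG**

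Section 6.1.4 lists the ECG ahead of the pre-dose PK sample and the final dose. If sites follow that order, both ECGs of the pair are pre-dose, and the change is not measured near the post-dose peak.

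**The case against.** The best defense has four parts.

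- **Detail is deferred.** Section 8.0 leaves detailed methodology to an SAP finalized before database lock. One sentence in the protocol is not a final decision, and it fixes no layout; a by-visit table would put Day 1 beside Day 29. This stands to the extent that the plan permits a poor summary without requiring one. It is also why the point is best settled now.
- **Adverse events cover the important cases.** Under Section 7.2, clinically significant ECG worsening from Baseline is reported as an AE or SAE and so feeds the TEAE tables. True, but it depends on case-by-case investigator judgment, and a modest shift in an arm's mean produces no event.
- **General rules apply.** Section 8.0 promises descriptive statistics for continuous variables and listings of all data. If intervals are in the database they will at least be listed. However, the rule does not promise change from Baseline, and no text says intervals are recorded after Screening.
- **ECG is not a named endpoint.** Section 2.2.2 lists ECG as a safety assessment, but its three endpoints are TEAEs/SAEs, laboratory changes and vital signs. This limits the importance of the point.

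A reader might infer more than the text supports:

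- **That the trial cannot show a QTcF change.** The gap is in the analysis text; the ECGs are scheduled in everyone.
- **That Day 43 percentages will be inflated, or that Day 43 causes old and new findings to mix.** No Day 43 percentage is planned, the conditional tracing is reasonable follow-up, and the mixing comes from the missing Baseline reference.
- **That 460/470 msec marks an on-treatment abnormality.** Those are Screening limits for subjects without ECG history.
- **That differing site readers drive the abnormal calls.** The documents do not say who reads the ECGs.

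**Conclusion.** The point holds as a gap in the planned ECG summary. Section 8.4.8 and the synopsis commit to abnormal ECGs only; as written, this neither separates new abnormalities from pre-existing ones nor shows a QTcF shift that stays short of an abnormal call. The AE route and the general rules in Section 8.0 narrow the gap without closing it.

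The size is illustrative, since the documents give neither the Baseline prevalence of abnormal ECGs nor an SD for QTcF change. If 20% or more of subjects entered with a persisting abnormality and 10% of the others developed a new one, about 70% or more of an arm's Day 29 count would be old. The interval summary would bring mean change into view, but only coarsely in arms of this size and, in the listed visit order, only pre-dose. It would not serve as a formal QT evaluation. This is a minor improvement that does not affect the trial's validity.

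**What to change.** Rewrite Section 8.4.8, carry the change into the synopsis, and detail it in the SAP before database lock:

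1. Summarize QTcF, PR and QRS at Baseline and Day 29/ET, with change from Baseline, by dose within formulation and combined placebo. Heart rate change is already covered under vital signs.
2. Add a Baseline-to-Day 29/ET shift table (normal/abnormal), with the number of new-onset abnormalities among subjects normal at Baseline.
3. Present Day 43 ECGs as a listing only, because they are taken only in subjects abnormal at Day 29 and have no usable denominator for late-onset findings.
4. Confirm that the eCRF captures the intervals at Day 1 and Day 29, and record the ECG time relative to dose so that the change can be interpreted.

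The cost is one or two more tables and a few eCRF fields. No additional visit or tracing is needed.

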8.4.9 Physical Examinations

Abnormal findings from full and symptom-directed physical examinations will be summarized and listed.

8.4.10 Protocol Deviations

Protocol deviations will be presented in a listing.

8.4.11 Treatment Compliance

Treatment compliance, based upon expected number of capsules to be used and actual number of capsules used, will be calculated and summarized.

8.4.12 Treatment Exposure

The total exposure to study drug will be calculated for each subject.

8.4.13 Missing Data

Only available data will be analyzed. There will be no imputation of missing data.

8.5 Statistical and Analytical Issues**8.5.1 Adjustment for Covariates**

Not applicable.

8.5.2 Interim Analyses and Data Monitoring

Not applicable.

8.5.3 Multicenter Study

Statistical analyses of efficacy and safety parameters will be based upon pooled data from all study centers.

8.5.4 Noncompartmental Analysis of Rifaximin and 25-desacetyl rifaximin

NCA will be conducted for subjects using intensive PK samples collected at Visit 2 (Day 1) and Visits 5 to 8 (Days 29 to 32). PK parameters listed in Section 8.4.4 will be summarized using descriptive statistics, including number of observations, mean, median, CV%, SD, minimum, and maximum.

9.0 STUDY ADMINISTRATION

9.1 Investigator Information and Training

The Investigators and essential support staff will be trained by Salix or designee on Good Clinical Practices (GCPs) and all aspects of protocol application and study management. It is the responsibility of the Investigator to ensure training of ancillary study staff. CANs assay examiners will be trained and certified on CANs assessment requirements using flow cytometry prior to screening patients (using healthy volunteers).

9.2 Monitoring

This study will be monitored by Salix or designee, in accordance with GCPs and applicable regulations. By signing this protocol, the Investigator agrees to periodic, on-site monitoring of all appropriate study documentation.

The progress of the study will be monitored by periodic on-site visits and frequent communications between the Sponsor or designee(s) and the Investigator (either by phone, fax, email, or post).

During these contacts, the monitor will:

- check and assess the progress of the study;
- review study data collected;
- conduct source document verification; and
- identify any issues and address their resolution.

The objectives of monitoring procedures are to verify that data are authentic, accurate, and complete; that the safety and rights of subjects are being protected; and that the study is conducted in accordance with the currently approved protocol (and any amendments), GCPs, and all applicable regulatory requirements.

9.3 Audits

At its discretion, Salix, or its designee, may conduct a quality assurance audit of this study. If such an audit occurs, the Investigator agrees to allow the auditor direct access to all relevant documents and to schedule his/her time and the time of his/her staff to permit meetings with the auditor to discuss findings and any relevant issues.

In addition, regulatory agencies may conduct a regulatory inspection of this study. If such an inspection occurs, the Investigator agrees to allow the inspector direct access to all relevant documents and to schedule his/her time and the time of his/her staff to permit meetings with the inspector to discuss findings and any relevant issues.

10.0 ETHICAL AND LEGAL ASPECTS

The Principal Investigator and the study staff are responsible for conducting this study in accordance with the applicable principles which have their origins in the Declaration of Helsinki, ICH, GCPs, and all other applicable laws and regulations.

This trial will be performed in compliance with the protocol and in accordance with Good Clinical Practice (International Conference on Harmonisation [ICH], Guidance E6), principles of human subject protection, and applicable country-specific regulatory requirements.

